12.4 Special categories, check all that apply

☐ Minors /Children	
■ Students	
▼ Employees - Civilian	
■ Employees - Contractor	
Resident/trainee	
☐ Cadets /Midshipmen	
Active Duty Military Personnel	
☐ Wounded Warriors	
☐ Economically Disadvantaged Persons	
Educationally Disadvantaged Persons	
Physically Challenged (Physical challenges include visual and/or auditory impairment)	
Persons with Impaired Decisional Capacity	
☐ Prisoners	
☐ Pregnant Women, Fetuses, and Neonates	
□ Non-English Speakers	
International Research involving Foreign Nationals - Headquarters Review is necessary	
You must also consider the requirements of DoDI 3216.02, paragraph 7.e.	
You must also consider the requirements of DoDI 3216.02, Enclosure 3, paragraph 7.e.	

12.5 Inclusion Criteria:

Order Number	Criteria
1	DEERS Eligible
2	Between the ages of 18-64 (inclusive) years
3	Able to read and understand English language for consent purposes
4	Currently experience pain in the bottom of your foot and/ or heel at any time during the day
5	Diagnosed with plantar fasciitis or plantar heel pain by a healthcare provider based on accepted diagnostic criteria
6	Able to commit to study procedures, including a 6-week intervention and 3-month follow-up?

12.6 Exclusion Criteria:

Order Number	Criteria	
1	History of traumatic injury to symptomatic foot/feet	
2	agnosed with a calcaneal (heel) fracture by a healthcare provider	
3	Previous surgery or other invasive treatment for same condition	
Significant portion of calf area covered in tattoos/ink/scarring (pigment in absorb light, causing overheating of skin)		
	Current use of pacemaker	

5	
6	History of neuropathy or inability to detect changes in skin temperature (increased risk of skin warming due to inability to detect change)
7	Current use of medications associated with sensitivity to heat or light (e.g., amiodarone, chlorpromazine, doxycycline, hydrochlorothiazide, nalidixic acid, naproxen, piroxicam, tetracycline, thioridazine, voriconazole)
8	Current or chronic sciatica resulting in chronic or intermittent lower extremity pain, numbness, or tingling
9	Concurrent participation in another research study addressing pain issue
10	Currently pregnant or plan to become pregnant during intervention period (safety of PBM not established in pregnancy)
11	Previous enrollment in this study for contralateral foot
12	Provider disagreement with any of the potential participant's screening answers
13	History of memory problems, dementia, and/or impaired decision-making ability
14	Any other medical condition that preclude safe participation in the study procedures

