All participants, regardless of study arm assignment, will be asked to complete the UC Protocol (Appendix H) which consist of a daily regimen of stretching and cryotherapy that includes 3-5 minutes of stretching upon waking, then approximately 3-5 minutes of stretching and 3-5 minutes of cryotherapy throughout the day, for the duration of 6 weeks (instructions and participant handout will be provided, Appendix I).

Participants will receive PBMT or sham-PBMT with the PBM device (Appendix J, Figure 1) over the course of three consecutive weeks (three treatments per week). PBM treatments will take

approximately 5-10 minutes to administer at each session. Specific treatment parameters will be based on measurements of calf, ankle, and foot using pre-calculated treatment tables; participants will receive 10 J/cm2, 25W output power, and the length of the treatment will be dependent on treatment area (size).

Photobiomodulation Therapy (PBMT):

PBMT will be administered by a trained member of the study team using the LightForce® XPi therapy laser, provided by LiteCure, LLC/DJO Global (New Castle, DE). The LightForce® XPi therapy laser is an FDA cleared device for the treatment of pain. The trained team members will use the Smart Hand Piece technology, which achieves effective treatments and improves dosing accuracy by assessing the operator's speed and providing real-time visual (red – amber – green light) and sensory feedback (Appendix J, Figure 2). The Smart Hand Piece is calibrated to shutoff when moving too slowly, and warn the operator when moving too fast by vibrating. The therapy is delivered through a flexible optical fiber threaded through the hand piece, which contains a rolling sapphire massage ball. The PBM therapy will be administered by rolling the massage ball over the plantar surface of the foot and dorsal aspect of the calf in contact with the participants' skin.

Sham-Photobiomodulation Therapy (Sham-PBMT):

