14.0 Risks and Benefits

14.1

Risks of Harm:

Identify all research-related risks of harm to which the subject will be exposed for each research procedure or intervention as a result of participation in this study. Consider the risks of breach of confidentiality, psychological, legal, social, and economic risks as well as physical risks. Do not describe risks from standard care procedures; only describe risks from procedures done for research purposes

Research Procedure Name: Photobiomodulation (PBM) Therapy Research Procedure Description: Light therapy for Plantar Fasciitis (PF)

The potential risks directly associated with study-specific activities and procedures are minimal. PBM treatment is used by a variety of healthcare practitioners for painful clinical conditions. Potential research-related risks include damage to eye structures and uncomfortable skin heating, which are both very rare.

Additionally, any time information is collected for a study, there is a small risk of breach of confidentiality.

14.2

Measures to Minimize Risks of Harm (Precautions, safeguards):

For each research procedure or intervention, describe all measures to minimize and/or eliminate risk of harms to subjects and study personnel

Protective eyewear will be worn by all participants and study team members during treatment sessions to avoid damaging their eyes.

All applicable study team members will complete a battery of training modules and hands-on training sessions to ensure safe operation of the PBMT device, and compliance with local laser safety requirements and American National Standards Institute (ANSI) standards Z136.1 (Safe Use of Lasers) and Z136.3 (Safe Use Lasers in Health Care). See Appendix K for the laser operator training plan.

A member of the research team will serve as a clinical laser safety officer (CLSO) to establish and manage the study-specific laser safety program. The designee will work with the MAMC Laser Safety Officer (LSO) and participate in the MAMC Laser Safety Committee (LSC) meetings quarterly to receive proper training. Along with the LSO and CLSO, the PI will ensure that the treatment space meets all regulatory requirements for utilization of a treatment laser, including appropriate signage and use of laser blocking screens to absorb any potential scatter/refraction of light outside of the treatment area.

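### Exclusion criterion 4 screens only the calf for extensive tattoos or ink, although the sole of the foot receives the same 25 W, 10 J/cm² contact laser: a minor safety gap that a few words would close.

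*Combined protocol and SAP*

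**What the plan says.** Criterion 4 in Section 12.6 excludes people with "Significant portion of calf area covered in tattoos/ink/scarring". Its parenthesis gives the reason: pigment absorbs light and the skin overheats. A few words of that parenthesis appear lost in the text supplied, but the part naming the calf is intact.

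Section 10.1 describes active treatment as "rolling the massage ball over the plantar surface of the foot and dorsal aspect of the calf", with the ball touching the skin. The setting is common to both sites: "participants will receive 10 J/cm2, 25W output power". No lower setting is given for the foot.

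Other parts of the protocol bear on the same risk:

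- Criterion 1 excludes "History of traumatic injury to symptomatic foot/feet".
- Criterion 3 excludes "Previous surgery or other invasive treatment for same condition".
- Criterion 6 excludes neuropathy or "inability to detect changes in skin temperature".
- Criterion 14 excludes any further medical condition that would make taking part unsafe.
- Section 10.1 adds a device safeguard: "The Smart Hand Piece is calibrated to shutoff when moving too slowly".
- Section 14.1 names the physical risks as "damage to eye structures and uncomfortable skin heating, which are both very rare".
- Section 14.2 provides that treatment is changed or halted if it becomes uncomfortably warm, requires operator training (Appendix K) and appoints a clinical laser safety officer.

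**The concern.** The criterion is narrower than its own reason. If heavily inked skin on the calf is unsuitable for this laser because it may overheat, the same holds for heavily inked skin on the sole, which is treated with the same ball at the same power and dose. As Section 12.6 reads, a person with extensive ink on the sole and none on the calf is not excluded by any criterion that mentions pigment.

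What is at stake is avoidable skin heating in a rare participant. Section 16.1 names rigorous screening as one of the ways in which the study's risks are prevented, so a hole in the screening list deserves a repair even when few people would fall through it.

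**Working it through.** The plan gives no figure on this point to reproduce. The check is mainly a comparison of texts, with two short calculations.

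**1. Is the foot a full treatment site?** Inputs from Section 10.1: 25 W, 10 J/cm², about 5 to 10 minutes per session.

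- Energy = power × time: 25 × 300 s = 7,500 J, and 25 × 600 s = 15,000 J.
- Area = energy ÷ dose: 7,500 ÷ 10 = 750 cm², and 15,000 ÷ 10 = 1,500 cm².
- The Background says the pilot gave half of each treatment to the foot, and Section 9.3 says dose is calculated here in the pilot's manner. If the even split is also kept (an assumption), the foot receives about 3,750 to 7,500 J per session.

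The foot is therefore not a marginal site, and the plantar fascia is the target tissue.

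**2. Does another criterion cover it?**

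| Safeguard | Plantar scarring | Plantar ink |
|---|---|---|
| Criterion 1 (foot trauma) | Covers scars from injury to the symptomatic foot | No |
| Criterion 3 (surgery or invasive treatment) | Covers scars from treating this condition | No |
| Criterion 6 (heat sensation) | Does not screen for it; ensures heat is felt | Same |
| Criterion 12 (provider disputes a screening answer) | Helps only if the question is asked | Same |
| Criterion 14 (other medical condition) | Plausibly covers scarring judged unsafe | Not clearly; a tattoo is not obviously a medical condition |
| Hand-piece shutoff | Responds to operator speed, not to the skin | Same |
| Modify-or-stop rule | Acts once warmth is uncomfortable | Same |

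Scarring is largely handled. Extensive plantar ink is not.

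**3. How many people could be concerned?** Section 11.4 puts about 50 in the active arm. If every sham participant crosses over, as Section 10.1 allows, up to 100 receive active laser. The expected number affected is N × p, where p is the proportion with a significant part of the plantar treatment area inked. The documents do not give p.

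- N × p stays below one if p < 1/50 = 2% with 50 treated, or p < 1/100 = 1% with 100 treated.
- For illustration only, taking p from 0.05% to 0.5%: 50 × 0.0005 = 0.025 at the low end, and 100 × 0.005 = 0.5 at the high end.

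**4. Would crossover catch it later?** No. Section 10.1 exempts crossover participants from repeat screening and from repeat baseline collection; only the pregnancy test is repeated. A skin check has to be made at the start, in both arms.

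**The case against.** The strongest reply is that this is an editorial matter. Eligibility is settled in person, staff measure the foot, and the plantar fascia is imaged before any laser is used, so extensive ink on the sole is unlikely to go unseen. Participants must be able to feel heat, trained operators use a hand piece with a speed cut-out, and treatment is changed or stopped for discomfort. The Background reports that the pilot treatment was well tolerated. The screening form (Appendix A), telephone script (Appendix M) and operator training plan (Appendix K) were not supplied and may already deal with pigment on the foot.

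Much of this stands, and it is why the point is minor. It does not remove the point. Seeing the ink is not the same as having a rule to act on it. The general safeguards apply to the calf as well, yet the protocol still chose to exclude extensive calf ink, and it gives no reason for treating the foot differently. The pilot account does not say whether anyone had plantar ink.

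The objection also succeeds on scarring. A reader might infer that scarred soles are as unprotected as inked ones. The documents do not support that: criteria 1, 3 and 14 cover most such cases, and the surviving rationale speaks of pigment only.

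**Conclusion.** The point holds as a minor participant-safety gap: criterion 4 omits a site to which its own reason applies, and the clear omission is extensive plantar ink. Small plantar tattoos are not at issue, since the criterion already accepts small ones on the calf.

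The number affected is probably below one. That rests on the assumption that fewer than 1 in 100 enrolled have extensive plantar ink, which the documents neither confirm nor contradict.

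Two stronger readings should be resisted. A reader might infer a definite chance that the trial will treat such a person, or that someone will be burned. With no prevalence given, the first cannot be stated; even if it could, it would measure exposure and not injury, and Section 14.1 describes uncomfortable heating as very rare. A reader might also infer damage to the trial's result. Nothing here affects power, bias or the analysis.

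The finding concerns Section 12.6 as written. If the appendices already ask about the foot, practice may be sound and only the criterion needs correcting.

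**What to change.** In criterion 4, replace *calf area* with *treatment area (calf or plantar foot of the study leg)* and keep the *significant portion* threshold.

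Have staff look at that skin when they take the baseline calf, ankle and foot measurements described in Section 10.1. This should be done in every participant and before randomisation, so that sham participants who later cross over are covered and nobody is excluded after allocation.

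Bring Appendices A, M and K into line if they differ. If the calf-only limit is deliberate, one sentence saying why the foot is exempt would settle the matter.

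The cost is a few words and a brief look during an existing procedure. The downside is possibly a rare extra exclusion; under the same assumption of fewer than 1 in 100, that is less than one person among 100 enrolled.

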13.0 Recruitment and Consent

13.1 Please describe the recruitment process, including how subjects will be identified and selected for the study.

Potential participants will be identified via four methods:

- Under the provisions of the Partial HIPAA Waiver, the local study team will review medical records of patients coming in to the Orthopaedic clinic for suspected plantar fasciitis to identify prospective research participants for the purposes of seeking their authorization to participate/use their protected health information for this research study. In these cases, the study team will receive approval from the potential participant's provider prior to approaching for possible study participation.
- 2. Direct referral from local healthcare providers in the local Family Medicine, Podiatry, Physical Therapy, and Physical Medicine & Rehabilitation clinics.
- 3. Patients may self-refer to participate in the study. Interested potential participants will be able to contact a member of the study team via phone or email. Potential participants who contact the study team directly will be instructed to access the Physical Therapy clinic or their primary care manager for a physical exam and diagnosis of PF, or confirmation of a previous PF diagnosis.
- 4. Study advertisements will be posted within the following locations, and copies will be provided to clinic staff:
 - a. Internal Medicine
 - b. Aviation Medicine
 - c. McChord Clinic
 - d. Winder Clinic
 - e. Okubo SCMH
 - f. Allen Soldier -Center Medical Home
 - g. SRL
 - h. Puyallup Community Medical Home
 - i. South Sound Community Medical Home
 - j. Armed Forces Wellness Center
 - k. Intrepid Spirit Center
 - I. Madigan Medical Mall

- m. Pharmacy waiting areas if possible
- n. Physical Therapy
- o. Physical Medicine and Rehabilitation
- p. Coffee bar
- q. Dining Facility entrance
- r. Intranet screen saver page

An appropriate Partial HIPAA Waiver application has been uploaded with this submission.

Participants may self-refer to the study. Interested potential participants will be able to contact a member of the study team (PI or RC) via phone or email. A process flowsheet can be found in Appendix O. Participants who contact the study team directly will be instructed to access the Physical Therapy clinic or their primary care manager for a physical exam and diagnosis of PF, or confirmation of a previous PF diagnosis. The Physical Therapy Clinic is a direct access clinic that does not require a referral.

Participants who are identified by clinic staff will be provided with information for contacting the study team.

The local research team will keep a separate electronic screening log containing DoD ID number, ineligible/eligible, and date screened. This log will be password protected and stored in a secure folder on a secure drive accessible only by authorized local research staff. This log is needed to avoid any duplicative screening of those that are screen failures or who decline study participation. This reduces burden on potential participants, providers, and study team members and ensures the study team will not screen the same person twice or examine records for eligibility criteria when screen status has already been already established.

13.2 Compensation for Participation:

Participants may receive \$60 to \$80 for their participation in this research. Participants that are initially randomized to the sham PBM group, and choose to crossover to receive active PBM and to stay in the study for an additional 6 weeks, are eligible for an additional \$20 for completing the study pain diary.

In accordance with the DoDI 3216.02, a federal employee (e.g. civil servant or Service member) completing a research activity while on duty will not be paid for their time spent taking part in that research activity. A federal employee completing a research activity while off duty will be paid for their time spent taking part in that research activity, following the schedule below.

Non-federal employees will be paid for their time spent taking part in research activities, following the schedule below.

There are four opportunities for receiving compensation:

- 1. when a participant completes the 3-week follow-up visit \$20
- 2. when a participant turns in the final pain diary on day 43 \$20,
- 3. when a participant completes the 3-month follow-up questionnaires \$20,
- 4. when a participant turns in the pain diary on day 43 post-elected crossover (only applicable to those initially randomized to the sham PBMT group that elect to crossover to receive treatment with active PBMT) \$20

Participants will receive payment in the form of a gift card or Visa-type card equivalent. Participants will only be paid for applicable research activities that they complete. They will not receive compensation for research activities they do not complete.

In order to receive compensation for participation in this research as a federal employee, a study team member will ask the participant to confirm they are off duty or on leave status in accordance with US Code Title 5, Section 6382. It will be the responsibility of the study participant to provide accurate information regarding their leave status at the appropriate compensation intervals. Upon request, the PI and/or authorized study team member may provide certification for intermittent leave, or leave on a reduced leave schedule, for planned study medical treatment(s) (in accordance with US Code Title 5, Section 6383).

13.3 Please describe the pre-screening process. If no pre-screening, enter Not Applicable in the text editor

This study has two screening phases: (1) Pre-screening based on initial inclusion/exclusion criteria (before informed consent), and (2) a formal screening phase to determine eligibility for randomization to intervention arm (after informed consent).

Pre-Screening (before consent):

If a potential participant expresses interest in learning more about the research study, a member of the research staff will briefly introduce the study, express the voluntary nature of participation, assess interest in participating, and screen the potential participant for eligibility. Eligibility will be determined in person using the Inclusion/Exclusion CRF (Appendix A). Individuals who do not meet Inclusion/Exclusion criteria will be encouraged to continue to seek care with their primary care provider and/or direct access at physical therapy.

Pre-screening conversations may also take place over the phone using the Screening Script (Appendix M). Potential participants who meet initial eligibility per the Screening Script and express interest in participating will be asked to come to clinic to complete an Inclusion/Exclusion CRF to confirm final eligibility with an authorized study team member prior to providing informed consent.

If the potential participant meets eligibility criteria as determined by the Inclusion/Exclusion CRF and expresses interest in participating, an authorized study team member will initiate the formal consent discussion and, if applicable, obtain informed consent. See protocol section 13.4 for additional information on the consent process.

Formal Screening (post-consent):

As part of the formal screening procedures, all consented participants that are biological females of child-bearing age and capacity will be required to complete a urine hCG pregnancy test. If the pregnancy test is positive, per the inclusion/exclusion criteria, the participant will be formally withdrawn from the study at this point, and will be encouraged to seek care with their primary care physician. If the pregnancy test is negative, the participant will be eligible to be randomized to a study arm and continue with the study procedures.

13.4 Consent Process: Revised Common Rule, Section 219.116: General requirements for informed sont whather written or eval are get forth in this navage

consent, whether written or oral, are set forth in this paragraph and apply to consent obtained in
accordance with the requirements set forth in paragraphs (b) through (d) of this section. Broad
consent may be obtained in lieu of informed consent obtained in accordance with paragraphs (b) and
(c) of this section only with respect to the storage, maintenance, and secondary research uses of
identifiable private information and identifiable biospecimens.

Are you requesting a w	aiver or alteration	of informed	consent?
------------------------	---------------------	-------------	----------

Please explain the consent process:

O Yes O No

Consent will be obtained in accordance with principles of Belmont Report and Common Rule auidelines.

The consent form will describe the purpose of the study, the procedures to be followed, and the risks and benefits of participation. A copy of the signed consent form will be given to the participant and the original will be stored in a locked cabinet inside of a locked office within the Podiatry Clinic. Documentation of consent will be recorded in the participant's medical record. No Legally Authorized Representatives will be utilized.

Formal consent, as represented by the act of signing a dated, IRB approved consent statement for the study will only occur after confirming eligibility using the Inclusion/Exclusion CRF, a thorough review of what is involved in the study, and after all questions have been answered. Potential participants will be provided information regarding all available study treatments and reminded of the expectations placed on them if they enroll, including the blinding and randomization processes.

The potential participant will be given a copy of the informed consent document to read before, during, and/or after discussion of the informed consent with the Research Coordinator, Principal Investigator, Associate Investigator, or other authorized study team member. Sufficient time will be given to the potential participant to understand the study purpose, study procedures, time commitments, potential risks and benefits, and the types of health information that will be accessed, collected, and used by the research team if they agree to participate in the study. Questions can be raised by the potential participant at any time during the consent discussion

and also at any time during the conduct of the study. The potential participant will be instructed that their participation is completely voluntary and that they may withdraw from the study at any time without penalty. Their decision to participate or to not participate, or to withdraw from the study after consent, will not affect their access to health care that they are otherwise entitled to and it will not affect their military position.

The authorized study team member present during the consent conversation will confirm that the potential participant has no additional questions before deciding to provide consent.

Every effort will be made to eliminate the perception of authority, which is a particularly important consideration when recruiting active-duty study participants. When applicable, the study investigators will be in scrubs or civilian clothes instead of uniform and will introduce themselves as doctor rather than their military rank. Some potential participants may be patients of the study PI or AI. In these cases, the consent conversation will be initiated by non-physician study staff to prevent any misconception of coercion or undue influence.

Informed consent and HIPAA authorization will be obtained in person.

In the event that there are significant new findings regarding the therapy that may affect participants' willingness to continue in the study, an information sheet will be provided to all current and past participants. The informed consent document will be amended for future participants.

Following completion of informed consent, the results of the Inclusion/Exclusion CRF will be entered into REDCap, an encrypted, access controlled, password protected electronic data capture and management system housed on a DoD server and maintained by the Uniformed Services University Information Technology (USU IT), and a unique study ID will be generated. This coded study ID will be used on all research data collection forms in place of the participant's name, Department of Defense (DoD) ID, or other protected identifier. No PII will be entered into REDCap. Please see Appendix R for additional information on REDCap.

13.5	DoDI 3216.02 requires an ombudsman to be present during recruitment briefings when research
	involves greater than minimal risk and recruitment of Service members occurs in a group setting. If
	applicable, you may nominate an individual to serve as the ombudsman.

N/A

Propose ombudsman

13.6 Withdrawal from Study Participation:

Explain the process for withdrawal and specify whether or not the subjects will be given the opportunity to withdraw their data their data/specimens in the event they wish to withdraw from the study

Participant Withdrawal:

Participants may withdraw from the study at any time without penalty. Participants will be informed that withdrawal will not affect their access to health care that they are otherwise entitled to and it will not affect their military position.

If a participant withdraws from the study, we may retain and analyze all coded/de-identified data collected up to the time of withdrawal if the data is necessary to maintain the integrity of the study. However, no further data will be collected after the date of withdrawal.

Participants may contact the study research coordinator/assistant or Principal Investigator to formally withdraw from the study. Participants will be advised to follow-up with their personal physician if they choose to withdraw.

Withdrawal Without Participant Consent:

A participant may be withdrawn from the study without their consent if remaining in the study might be dangerous or harmful to them. Participation may also be stopped if the military mission requires it, if they lose their right to receive medical care at a military hospital, if the study is canceled, if they fail to adhere to the protocol and/or therapy plan, or if they display inappropriate behavior towards study personnel.

The reason for any withdrawal/removal will be documented.

